8.3.2.2 Device Malfunction

For the purposes of this trial, it is expected that device malfunctions will be observed by either the investigator or subject. In both cases, these will be reported to the call center and processed as described in Section 6.2.2 for PQCs and product nonconformances.

8.3.2.3 Unanticipated Adverse Device Effects

An unanticipated device adverse effect includes any serious adverse effect on health or safety or any life-threatening problem or death caused by, or associated with, a device, if that effect, problem, or death was not previously identified in nature, severity, or degree of incidence. Any unanticipated device adverse effect must be reported by fax or e-mail to the sponsor or designee using the contact information on the cover page of this protocol as soon as the trial site personnel are made aware of an event (within 24 hours). The sponsor will review all malfunctions and determine if they are unanticipated adverse device effects, and report to regulatory or other bodies (as appropriate).

8.3.2.4 Immediately Reportable Events

Immediately Reportable Event:

- Any SAE (Note: all SAEs whether anticipated or not must be reported to the sponsor or sponsor's designee as immediately reportable events [IREs])
- Pregnancies are also defined as IREs. If the subject becomes pregnant during the trial, the subject should be discontinued. Pregnancy will only be documented on the AE eSource if there is an abnormality or complication. This does not include pregnancy of the partner of the subject.
- Any UADE

The investigator must immediately report (within 24 hours), using an IRE form, after the investigator or site personnel become aware of any IRE (SAE, confirmed pregnancy, or UADE), by fax or e-mail to the sponsor or designee using the contact information on the cover page of this protocol (Please note that the IRE form is NOT the AE eSource.).

Subjects experiencing SAEs should be followed clinically until their health has returned to baseline status, or until all parameters have returned to normal or have otherwise been explained. It is expected that the investigator will provide or arrange appropriate

Protocol No. 345-201-00002

supportive care for the subject and will provide prompt updates on the subject's status to the sponsor.

8.3.3 Procedure for Breaking the Blind

The investigator is encouraged to contact the sponsor/clinical research organization (CRO) medical advisor to discuss their rationale for unblinding. However, to prevent delays to the investigator or medical personnel responding to a potentially emergent situation, unblinding of CT-152 or sham will not be dependent upon the investigator receiving approval from the sponsor/CRO medical advisor (ie, the investigator will be able to obtain the code break information independent of the sponsor/CRO medical advisor). The investigator must contact the sponsor/CRO medical advisor by telephone or e-mail with an explanation of the need for opening the treatment assignment code within 24 hours of opening the code. If the blind is broken, the Global Pharmacovigilance Department must be notified immediately (see the cover page of this protocol for contact information). Documentation of breaking the blind should be recorded in the subject's medical record with the date and time the blind was broken and the names of the personnel involved. Once the blind is broken for a subject, that subject may not reinitiate treatment with CT-152 or sham.

8.3.4 Follow-up of Adverse Events

8.3.4.1 Follow-up of Nonserious Adverse Events

Nonserious AEs that are identified at any time during the trial must be recorded on the AE eSource with the current status (ongoing or resolved/recovered) noted. All nonserious events (that are not IREs) that are ongoing at the last scheduled contact will be recorded as ongoing on the eSource. For any AE having been identified throughout the trial, during analysis, additional relevant medical history information may be requested by the sponsor to further ascertain causality (including, but not limited to, information such as risk-related behavior, family history and occupation).

8.3.4.2 Follow-up of Immediately Reportable Events

This trial requires that subjects be actively monitored for IREs up to 28 calendar days after the last subject visit or contact.

Immediately reportable events that are **identified or ongoing at the last scheduled contact** must be recorded as such on the AE eSource and the IRE form. If updated information (eg, resolved status) on IRE status becomes available after a subject's last scheduled contact (up to the last remote visit or telephone contact for the entire trial), this

Protocol No. 345-201-00002

must be reported to the sponsor and recorded in the AE eSource and the IRE form, according to the appropriate reporting procedures described in Section 8.3.2.4.

It is expected that the investigator will provide or arrange appropriate supportive care for the subject and will provide prompt updates on the subject's status to the sponsor. The investigator will follow IREs until the events are:

- resolved.
- stabilized,
- the subject is lost to follow-up, or
- has died.

[figure not shown]
Resolution means that the subject has returned to the baseline state of health and stabilized means that the investigator does not expect any further improvement or worsening of the subject's condition. The investigator will continue to report any significant follow-up information to the sponsor up to the point the event has resolved or stabilized, or the subject is lost to follow-up, or has died.

Refer to Section 10.3 for additional information regarding the follow-up period for subjects that become pregnant.

8.3.4.3 Follow-up and Reporting of Immediately Reportable Events Occurring After Last Scheduled Contact

Any new IREs reported to the investigator which occur after the last scheduled contact and are determined by the investigator to be reasonably associated with the use of CT-152 or sham, should be reported to the sponsor according to the procedures outlined in Section 8.3.2.4. This may include IREs that are captured on follow-up telephone contact or at any other time point after the defined trial period and continue to report any significant follow-up information to the sponsor until the events are resolved or stabilized, or the subject is lost to follow-up or has died.

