^jAdverse events will be collected from the signing of the informed consent document through the last subject visit or contact. Serious adverse events will be collected from the signing of the informed consent through and including 28 calendar days after the last use of CT-152 or sham.

^kSubject debriefing will occur at the conclusion of a subject's participation in the trial and after all final visit procedures have been completed.

Protocol No. 345-201-00002

2 Introduction

CT-152 is a prescription digital therapeutic intended for the treatment of major depressive disorder (MDD) in adults. It is intended for use as an adjunct to standard of care (pharmacotherapy) and under the supervision of a clinician. The current trial is designed to provide data regarding effectiveness and safety for CT-152.

CT-152 is being co-developed by Otsuka Pharmaceutical Development & Commercialization, Inc. and Click Therapeutics, Inc.

This trial will evaluate the effectiveness of CT-152 in reducing depressive symptoms in adult subjects diagnosed with MDD who are on antidepressant therapy (ADT) monotherapy. CT-152 delivers an interactive, software-based intervention featuring cognitive-emotional training, psychotherapy lessons, psychotherapy messages, and engagement messages. CT-152 will be evaluated relative to a sham arm which will serve as a control that deploys only a working memory exercise. In order to retain the placebo nature of the sham, it will not include psychotherapy content.

Abbreviations used are listed in Section 10.5.

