At the conclusion of Week 10 or at early discontinuation early from the trial, a debriefing session will occur with the subject. Trial site staff will describe the components of each digital therapeutic and discuss the trial hypothesis, (ie, that one digital therapeutic was hypothesized to be more beneficial in improving depression symptoms based on a small study conducted previously). Trial site staff should explain that a trial (ie, the one in which they participated) was needed to further evaluate these initial findings. Subjects will be told the reason for the hypothesis blinding, ie, subjects would be less likely to question the efficacy of the treatment in which they were assigned. Adequate protective measures and resources will be available in the instance a subject is adversely affected by

Protocol No. 345-201-00002

the withheld information. Trial site staff will be provided with debriefing guidelines to assist in these discussions with the subjects.

All results from assessments should be recorded in eSource.

For this trial, only individuals who have been properly trained may administer the clinician-administered scales. Assessments for the M.I.N.I., HAM-D₁₇, C-SSRS, and CGI-S will be administered by the trial sites using the provided scales. Training on the administration of these assessments will be conducted.

No ratings as part of trial assessments may be performed by a rater prior to approval by sponsor and completion of rater training/certification. It is preferred that as often as possible, for each subject, the site-administered scales be performed by the same person throughout the trial.

The GAD-7, PHQ-9, WHODAS 2.0, CCl will be completed by the subject electronically. The subjects will be encouraged to complete the assessments prior to but within the window of the scheduled remote visit. All subject self-assessments should be reviewed and verified by the trial site for completeness during the remote visit, or within the window of the remote visit.

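### Protocol Section 8.3.4.3 makes reporting of new IREs after the last scheduled contact depend on causality, in conflict with the unconditional 28-day monitoring in Section 8.3.4.2

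*Protocol*

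**What the plan says.** Five places in the protocol bear on an SAE that arises late.

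- **Section 8.3.2.4** makes every SAE an IRE and says that "all SAEs whether anticipated or not must be reported to the sponsor". It states no time limit and no causality condition. Pregnancies and unanticipated adverse device effects are IREs too.
- **Section 8.3.4.2** requires that subjects be "actively monitored for IREs up to 28 calendar days after the last subject visit or contact". Its recording instruction, however, deals with IREs already identified or ongoing at the last scheduled contact.
- **Section 8.3.4.3** deals with new IREs that "occur after the last scheduled contact and are determined by the investigator to be reasonably associated with the use of CT-152 or sham". It mentions events picked up on a follow-up telephone contact and sets no starting point later than the last scheduled contact.
- **Section 1.3, Table 1.3-1, footnote j** has SAEs collected from consent "through and including 28 calendar days after the last use of CT-152 or sham". This 28-day count starts at last use, not at last contact.
- **Section 10.3** has any pregnancy notified for 28 days after the last remote visit or contact, with no relatedness test.

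On the analysis side, SAP Section 9.1 lists SAEs by subject and gives no cut-off. SAP Section 9.1.1 takes adverse events before the extension starts. SAP Section 9.1.2 ends the extension-period tables at the last visit or contact in that period.

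**The concern.** For a new SAE after the last scheduled contact, Section 8.3.4.3 is the only specific instruction that a site has, and it asks for a causality opinion before reporting. A relatedness condition of this kind usually begins once the unconditional reporting period is over. Here it begins on that period's first day.

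The events most exposed are those that a safety evaluation in depression should not miss. Section 8.3.1 gives worsening depression and suicidality as examples of SAEs, and Section 8.3.2.1 calls worsening of MDD symptoms anticipated in this population. A hospitalisation or suicidal crisis after the final visit is easily put down to the illness, and a site following 8.3.4.3 could then leave it unreported to the sponsor.

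The condition is also loosely defined. Section 8.3.1 defines causality only in relation to CT-152, whereas 8.3.4.3 speaks of association with CT-152 or sham and uses different words for it. In addition, Table 1.3-1 schedules no contact after Week 10, so nothing in the schedule carries the active monitoring.

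**Working it through.** The plan states no figure on this point, so there is none to reproduce. The check compares the texts and counts days.

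**Step 1: do the sections overlap?** Section 8.3.4.2 covers the 28 days after the last visit or contact, without a condition. Section 8.3.4.3 starts at the last scheduled contact, with a condition. If these are the same contact, the first 28 days covered by 8.3.4.3 are exactly those of 8.3.4.2. Pregnancy shows that the two rules cannot both stand: Section 10.3 wants any pregnancy in that window notified, while under 8.3.4.3 the same event would qualify only if it were judged associated with an app.

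**Step 2: how many days are affected under each anchor?** Let U be the day of last use and C the day of last contact. For an early terminator, C is taken as the early-termination visit.

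- Window A (footnote j) ends on day U + 28. Days of A after last contact = max(0, U + 28 − C).
- Window B (Section 8.3.4.2) ends on day C + 28. Days of B after last contact = 28 in every case.

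Inputs: sessions are scheduled over six weeks, to Day 42 (Section 6.1.1). Week 10 is Day 70 with a window of ±3 days (Table 1.3-1). After Week 6 both memory tasks are withdrawn, but CT-152 subjects may still open earlier psychotherapy content (Section 6.1.1). The early-termination days are assumed examples.

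| Subject | U | C | A ends | Days of A after C | B ends | Days of B after C |
|---|---|---|---|---|---|---|
| Completer | 42 | 70 | 70 | 0 | 98 | 28 |
| Completer, visit 3 days early | 42 | 67 | 70 | 3 | 95 | 28 |
| Completer, visit 3 days late | 42 | 73 | 70 | 0 | 101 | 28 |
| CT-152 completer, lessons opened to Day 70 | 70 | 70 | 98 | 28 | 98 | 28 |
| Early terminator | 14 | 14 | 42 | 28 | 42 | 28 |
| Early terminator | 14 | 21 | 42 | 21 | 49 | 28 |
| Early terminator | 35 | 38 | 63 | 25 | 66 | 28 |

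The conflict with 8.3.4.2 is therefore 28 days for everyone. For a Day 70 completer that is Days 71 to 98, or 28/98 = 29% of the days from Day 1 to the end of window B. The conflict with footnote j is 0 to 3 days for a completer whose last use was Day 42. It is 21 to 28 days in the other examples.

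**Step 3: where would a missing report show?**

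- *Sponsor reporting:* affected, because this is what 8.3.4.3 governs.
- *By-subject SAE listing (SAP 9.1):* affected, because it has no cut-off and an unreported event cannot be listed.
- *Extension-period TEAE tables (SAP 9.1.2):* not affected for completers. A Day 71 to 98 event falls outside them whatever the causality opinion.
- *Treatment-period tables (SAP 9.1.1):* possibly affected for subjects who leave before the extension, since no end date is stated for them.

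**The case against.** The strongest reply is that Section 8.3.2.4 still governs. It is mandatory and unfiltered, and 8.3.4.3 says only that associated events should be reported, without exempting the rest. A site that reads both would report everything. This stands as far as it goes: a reporting gap is a risk that follows from the restrictive wording, not something the protocol orders. It does not remove the conflict, because the condition has no function unless it narrows reporting.

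A second reply is that the weeks after the sessions end are already well covered for completers. Adverse events are collected without a causality condition at Weeks 7, 8, 9 and 10, and the C-SSRS is given at Weeks 8 and 10. That is correct. The affected days for a completer come after those four weeks.

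Three stronger readings are tempting, and the documents do not support them.

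- *A reader might infer that the condition decides which late SAEs are counted in each arm and so biases the comparison.* For completers the extension tables have already closed. The documents give no SAE rates and no basis for a causality opinion that differs by arm, so neither size nor direction can be derived.
- *A reader might infer that the judgement is made unblinded, because it follows debriefing.* At debriefing, "Trial site staff will describe the components of each digital therapeutic and discuss the trial hypothesis". That covers both apps and is not a code break under Section 8.3.3. Section 6.3 accepts that site staff may become unblinded, but that applies to causality opinions during treatment as well.
- *A reader might infer that the protocol has a single 28-day rule for all SAEs.* It has two anchors, and Section 8.3.2.4 states no window at all.

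**Conclusion.** The contradiction is real. Within the 28 days after the last visit or contact, Section 8.3.4.3 attaches a relatedness condition to new IREs that Sections 8.3.4.2, 8.3.2.4 and 10.3 do not have. With Section 8.3.4.2 it affects every subject. With footnote j it matters mainly for early terminators and for CT-152 subjects who use lessons in the extension.

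The consequence is possible under-reporting of late SAEs to the sponsor and gaps in the SAE listing. Treatment-period tables may also be incomplete for subjects who leave early. The conclusion assumes that the last scheduled contact is the subject's last visit or contact, and that a site may follow the specific instruction over the general one. No number of lost events can be given. The primary efficacy analysis is untouched, but a pivotal trial with a safety objective should correct this.

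**What to change.** 1. Reword Section 8.3.4.3 so that its relatedness condition applies only to IREs occurring after the 28-day period of Section 8.3.4.2. Say that every SAE inside that period is reported regardless of causality.
2. State one anchor for the 28 days and use it in footnote j, 8.3.4.2 and 8.3.4.3. The last visit or contact already serves in 8.3.4.2 and 10.3. A last-use anchor can give the arms different windows, since only CT-152 keeps usable content after Week 6.
3. State in SAP Section 9.1 whether SAEs in that window are tabulated or only listed. Give SAP Section 9.1.1 an end date for subjects who never enter the extension.

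The cost is one sentence in a protocol amendment, conforming edits in the protocol and SAP, and a few more SAE forms. A telephone contact at the end of the 28 days would give the active monitoring a scheduled occasion, but it is optional and the correction does not depend on it.

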8.4 Other Assessments

Protocol No. 345-201-00002

8.4.3 Mini International Neuropsychiatric Interview

The M.I.N.I. (Version 7.0.2 for DSM-5) will be used as a tool for conducting a structured interview for eligibility assessment at the screening visit (Table 1.3-1).

The M.I.N.I. is a widely used structured diagnostic interview instrument developed for DSM-5 psychiatric disorders. A qualified rater will conduct the interview.

The results of the M.I.N.I. will be compared with the inclusion/exclusion criteria for evaluation of comorbid diagnoses.

8.4.4 **Antidepressant Treatment Response Questionnaire**

The MGH-ATRQ will be used to collect a subject's history of pharmacological treatment for their current episode. It will be administered at screening as part of the collection of the subject's psychiatric history and will be utilized to determine eligibility for entry into the trial.

8.4.5 Hamilton Rating Scale for Depression, 17-Item

The HAM-D₁₇ will be administered by trial site staff at the time points described in the schedule of assessments (Table 1.3-1) as part of the eligibility assessments.

The HAM-D₁₇ will be administered utilizing the Structured Interview Guide for the Hamilton Depression Rating Scale (SIGH-D). Detailed instructions for administration of this structured interview will be provided.

8.4.6 **Diagnostic Criteria for Major Depressive Disorder**

The subject's DSM-5 diagnosis of MDD, based on the clinical interview and medical/psychiatric history and confirmed by the M.I.N.I., should be documented in eSource.

Protocol No. 345-201-00002

8.4.7 Urine Drugs-of-Abuse Screen

Urine drugs-of-abuse screens will be performed by the subject after signing the informed consent and before the baseline visit on Day 1. Additional tests may be required for further evaluation at unscheduled time points as warranted by investigator judgment.

If the screening visit is performed in person, the urine drugs-of-abuse screen will be performed at the trial site.

If the screening visit is performed remotely, urine drug screen test kits and instructions will be provided to the trial sites to ship to the subject after the informed consent is signed. The subject is to perform the test and provide evidence of the test result to the trial site staff. Details can be found in the Site Operations Manual.

Alternative methods of test performance/acquisition may be able to be accommodated following discussion with medical monitor.

Subjects with a positive urine drug screen resulting from use of cannabis, or prescription or over-the-counter medications, or products that, in the investigator's documented opinion, do not signal a clinical condition that would impact the safety of the subject or interpretation of the trial results may continue evaluation for the trial following consultation and approval by the medical monitor. However, subjects will be instructed not to use cannabis products during the trial as per Section 6.5.1, as it may impact the potential efficacy of the digital intervention. The investigator may retest a subject if it is believed a positive urine drug screen is a false positive test, following discussion with the medical monitor.

See Section 10.2 for the list of drugs-of-abuse that will be tested for.

8.4.8 Pregnancy Test

Females of childbearing potential will perform a urine pregnancy test after signing the informed consent and before the baseline visit on Day 1.

If the screening visit is performed in person, the urine pregnancy test will be performed at the trial site.

If the screening visit is performed remotely, urine pregnancy test kits and instructions will be provided to the trial sites to ship to the subject after informed consent is signed. The subject is to perform the test and provide evidence of the test result to the trial site staff. If the test result is positive, the subject is to repeat the test in 2 days (> 48 hours from first test) and provide evidence of the repeat test result to the trial site staff. Details can be found in the Site Operations Manual.

Protocol No. 345-201-00002

Alternative methods of test performance/acquisition may be able to be accommodated following discussion with the medical monitor.

A confirmed positive pregnancy test result after signing the informed consent and before the baseline visit on Day 1, will require exclusion of the subject. A positive pregnancy test after the baseline visit will require discontinuation of the subject from the trial.

See Section 10.3 for contraceptive guidelines and collection of pregnancy information.

9 Statistical Considerations

9.1 Sample Size

The initial sample size is calculated to detect a 3-unit difference between CT-152+ADT and sham+ADT in the change from baseline in MADRS total score with 85% power at a 2-sided $\alpha = 0.05$ level, assuming a common standard deviation of 9. The resulting sample size is 324 evaluable subjects in total (162 subjects in each arm). To compensate for subjects that fail to have evaluable assessments of MADRS total score in the full analysis set (FAS) sample (estimated at up to 10% of all subjects), a total of 360 subjects (180 subjects in each arm) will be randomized in this trial.

Due to the limitations of applying assumptions on the treatment effect size, and in order to ensure adequate power of the trial, an unblinded interim analysis will be conducted by a Data Monitoring Committee (DMC; see Section 9.5.1). The final sample size could be increased to 540 subjects (270 subjects in each arm) as per recommendation of the DMC. Using the O'Brien-Fleming spending function⁴⁹ a significance level of 0.003 (2-sided) is allocated to this interim analysis. The corresponding final significance level is 0.049 (2-sided).

The trial will randomize eligible subjects 1:1 across approximately 50 trial sites. The sample size at any single trial site will be capped at approximately 15% of the total number of randomized subjects. Randomization will be stratified by trial site.

